## **7. TREATMENT COMPLIANCE**

Study drug (daratumumab) will be administered by qualified site staff, and the details of each administration will be recorded in the electronic case report form (eCRF). Additional details are provided in the SIPPM or equivalent document.

## **8. CONCOMITANT THERAPY**

Throughout the study, investigators may prescribe any concomitant medications or treatments deemed necessary to provide adequate supportive care except for those listed in Section 8.2. The sponsor must be notified in advance (or as soon as possible thereafter) of any instances in which prohibited therapies are administered.

Routine systemic use of the following concomitant medications will be collected in the eCRF and recorded in the source documents beginning with signing of the ICF to 30 days after the last dose of the last study treatment or until the start of subsequent anticancer treatment, if earlier: growth factors, transfusions, anti-infectives (antibacterials, antivirals, and antimycotics), steroids, anti-arrhythmics and other cardiac supportive therapy, anti-epileptics, centrally acting psychiatric medication, anti-histamines and other medications targeting post-dose systemic reactions, bisphosphonates, and any anticancer therapy (including radiation). Concomitant medications to manage AEs and SAEs will be recorded as per Section 12.3.1.

### **8.1. Permitted Therapies**

Supportive management for infections is strongly recommended, including vaccination with pneumococcal vaccine before beginning treatment with daratumumab. Management of IRRs is also recommended, as discussed in Section 6.4. Other symptoms may be managed according to institutional guidelines provided medications that could potentially prolong the QT interval are not administered (see Section 8.2).

Vaccination is allowed per local guidelines (see Section 8.2 for Prohibited Therapies).

### **8.2. Prohibited Therapies**

For subjects in the QTc substudy, medications with known or possible risk of torsades de pointes (see <https://www.crediblemeds.org>) are prohibited during Cycle 1. Use of such medications may result in the subject becoming unevaluable for the assessment of potential effects of daratumumab on QT.

Use of the treatments listed below is prohibited during the study:

- Administration of approved or investigational treatments for SMM or/and MM (including but not limited to conventional chemotherapies, immunomodulatory drugs (IMiDs), or proteasome inhibitors).

- Other agents that target CD38

Administration of live attenuated and replication-competent viral vector vaccines are prohibited.

### 8.3. Management of Hepatitis B Virus Reactivation

Primary antiviral prophylaxis is permitted as per local standard of care. Per protocol, HBV DNA testing by PCR is mandatory for subjects at risk for HBV reactivation see Section 9.5.2.

For subjects who are diagnosed with HBV reactivation while on treatment, study treatment should be interrupted until the infection is adequately controlled. If the benefits outweigh the risks, study treatment may be resumed with concomitant antiviral prophylaxis as per local standard of care. Consult a liver disease specialist as clinically indicated.

## 9. STUDY EVALUATIONS

### 9.1. Study Procedures

#### 9.1.1. Overview

The Time and Events Schedule ([Table 1](#)) summarizes the frequency and timing of efficacy, PK, immunogenicity, biomarker, and safety measurements applicable to this study. As of Amendment 5, refer to [Attachment 4](#) for a description of study procedures for subjects who continue in the Treatment Extension Phase or who have discontinued treatment but remain in Follow-up.

Blood collections for PK assessments should be kept as close to the specified time as possible. Other measurements may be done earlier than specified timepoints if needed. Actual dates and times of assessments will be recorded in the source documentation.

Additional serum or urine pregnancy tests may be performed, as determined necessary by the investigator or required by local regulation, to establish the absence of pregnancy at any time during the subject's participation in the study.

The maximum blood volume for the study is estimated at approximately 25 mL during screening and 340 mL during the first year. In the Follow-up Phase, subjects prior to PD will continue to have approximately 20 mL blood drawn every 2 months for serum disease evaluations. This includes laboratory assessments associated with safety, efficacy, and PK evaluations, as well as scientific research samples. Repeat or unscheduled samples may be taken for safety reasons or for technical issues with the samples.

#### 9.1.2. Screening Phase

The signed ICF must be obtained before any study-specific procedures are performed. The Screening Phase begins when the first protocol specified screening assessment is performed (typically signing of the ICF). During the Screening Phase, eligibility criteria will be reviewed and a complete clinical evaluation will be performed as specified in [Table 1](#). Screening procedures will be performed within 28 days before randomization; however, chest x-rays and 12-lead ECGs

performed up to 42 days before randomization and imaging (skeletal radiography, low-dose CT, or MRI) and bone marrow aspirate/biopsy performed up to 56 days before randomization as routine standard of care for the subject's disease can be used.

Eligibility of the subject is based on central laboratory results of screening serum and urine M-protein measurements.

### 9.1.3. Treatment Phase

Details of the procedures performed during the Treatment Phase (including treatment extension or treatment re-initiation) are outlined in [Table 1](#). As of Amendment 5, refer to [Attachment 4](#) for a description of study procedures for subjects who continue in the Treatment Extension Phase or who have discontinued treatment but remain in Follow-up. Subjects should start study treatment within 5 days after randomization. A window of  $\pm 5$  days is allowed for visits to the clinic. The start of each cycle should be scheduled relative to Cycle 1 Day 1 and should not change if visits have shifted within the allowed window. Subjects will be closely monitored for AEs, laboratory abnormalities, and clinical response. Clinical evaluations and laboratory studies may be repeated more frequently, if clinically indicated. If disease progression is diagnosed, then the subject will discontinue study treatment, complete the End-of-Treatment Visit, and enter the Follow-up Phase.

For subjects in Arm A (long intense) and Arm B (intermediate), there is a possibility to extend treatment with IV daratumumab (Q8W) after the end of Cycle 20 if, as per investigator discretion, there is a positive benefit/risk ratio, absence of Grade  $\geq 3$  treatment related toxicity, and at least stable disease has been achieved. In the case of subjects who already completed EOT and end of Cycle 20 occurred  $< 6$  months, these subjects can also continue receiving IV daratumumab administrations every 8 weeks. For subjects continuing in the Treatment Extension Phase as of Amendment 5, daratumumab 16 mg/kg IV may be switched to daratumumab 1800 mg SC at the discretion of the investigator at the same dosing (Q8W) schedule. Subjects with a known allergy/intolerance to sorbitol will not be eligible to switch to daratumumab SC.

### End of Treatment Visits

Unless a subject withdraws consent for study participation or is lost to follow up, an End-of-Treatment Visit is to occur at 28 days  $\pm 7$  days after the last dose of all study treatments. Every effort should be made to conduct the End-of-Treatment Visit before the subject starts subsequent treatment. If a subject is unable to return to the site for the End-of-Treatment Visit, then the subject should be contacted to collect information on AEs and concomitant medications that occur up to 30 days after the last dose of study treatment. Additional information on reporting of AEs is presented in [Section 12](#). Due to the addition of the treatment extension outlined in Amendment 4 which allowed some subjects to resume daratumumab treatment if within 6 months of last dose of Cycle 20, it is possible for subjects to have 2 EOT visits associated with this study. As of Amendment 5, this additional EOT visit associated with treatment extension should be conducted as specified in [Attachment 4](#).

As such, 2 EOT visit CRFs should be completed as applicable for subjects who continued to treatment extension (End of Treatment CRF and End of Treatment Extension CRF).

#### 9.1.4. Follow-up Phase

The Follow-up Phase will begin once subjects complete the planned number of cycles, and no treatment extension will be given as per investigator's discretion. In case of treatment extension or treatment re-initiation, the same procedures are to be followed as outlined in Section 9.1.3 and Table 1 (as of Amendment 5, refer to Attachment 4). If included in the treatment extension, it is possible that subjects will have 2 Follow-up Phase portions of the study (1 after the planned 20 cycles, and 1 after the last dose in the treatment extension). As of Amendment 5, these additional protocol-specified Follow-up assessments should be conducted as specified in Attachment 4.

Reasons for premature discontinuation of study treatment are listed in Section 10.3. Subjects who discontinue before disease progression must continue to have disease evaluations at Week 5, Week 9, and then every 8 weeks for the first year, thereafter every 16 weeks according to the Table 1 (as of Amendment 5, refer to Attachment 4) until confirmed PD, death, the start of a new anticancer therapy, withdrawal of consent, lost to follow-up, or the end of the study. If subjects have not progressed to symptomatic MM, no other treatment for SMM or MM is allowed during the study. After progressive disease, follow-up for subsequent multiple myeloma therapy (including the response to the first subsequent multiple myeloma therapy), second primary malignancies, and survival status will be obtained at least every 6 months.

If the information is obtained via telephone contact, written documentation of the communication must be available for review in the source documents. If the subject has died, the date and cause of death will be collected and documented in the eCRF.

The end of the study will occur up to approximately 7 years after the last subject's first dose, following a decision by the sponsor to end the study based on data from the smoldering multiple myeloma Phase 3 study (SMM3001), or for reasons outlined in Section 17.9.2, whichever occurs first.

#### 9.2. Efficacy

As of Amendment 5, refer to Attachment 4 for a description of study procedures for subjects who continue in the Treatment Extension Phase or who have discontinued treatment but remain in Follow-up. Disease assessments will be performed at Week 5, Week 9, and then every 8 weeks in the first year, thereafter every 16 weeks (including treatment extension/re-initiation phase) until disease progression. A window of  $\pm 7$  days before the scheduled assessment date is allowed. For subjects with treatment delays, disease assessments should be performed at the time of daratumumab administration, but do not need to be repeated if they were performed within 14 days before the actual treatment date. Disease progression, if based on laboratory results only, must be confirmed by a consecutive assessment.

Disease assessments will be performed by a central laboratory (unless otherwise specified) according to Table 1. Disease progression to symptomatic MM will be evaluated using the IMWG criteria (Rajkumar 2014). For subjects who discontinue study drug before disease progression, disease assessments should continue to be performed as scheduled until disease progression, death,

withdrawal of consent for study participation, or the end of the study. Disease assessments scheduled for treatment days should be collected before study drug is administered.

### 9.2.1. Evaluations

As of Amendment 5, refer to [Attachment 4](#) for a description of study procedures for subjects who continue in the Treatment Extension Phase or who have discontinued treatment but remain in Follow-up. The text that follows in the subsections of 9.2.1 describes the evaluations required prior to Amendment 5.

#### 9.2.1.1. Assessment of Response

Disease evaluations must be performed as outlined in the Time and Events Schedules on the scheduled assessment day ( $\pm 7$  days). Disease evaluations scheduled for treatment days should be collected before study drug is administered. Disease evaluations will be performed by a central laboratory (unless otherwise specified).

This study will use the IMWG consensus recommendations for MM treatment response criteria (Durie 2007; Rajkumar 2011) presented in [Table 4](#). For quantitative immunoglobulin at baseline, M-protein, and immunofixation measurements in serum and 24-hour urine, the investigator will use results provided by the central laboratory.

**Table 4: International Uniform Response Criteria Consensus Recommendations**

| Response  | Response Criteria   |
|---|---|
| Stringent complete Response (sCR)   | 
 
CR as defined below, plus
 
Normal FLC ratio, and
 
Absence of clonal PCs by immunohistochemistry, immunofluorescencea or 2- to 4-color flow cytometry
 
   |
| Complete response (CR)*   | 
 
Negative immunofixation on the serum and urine, and
 
<5% PCs in bone marrow
 
   |
| Very good partial Response (VGPR)*  | 
 
Serum and urine M-component detectable by immunofixation but not on electrophoresis, or
 
<math>\geq 90\%</math> reduction in serum M-protein plus urine M-protein <100 mg/24 hours
 
  |
| Partial response (PR)   | 
 
<math>\geq 50\%</math> reduction of serum M-protein and reduction in 24-hour urinary M-protein by <math>\geq 90\%</math> or to <200 mg/24 hours
 
If the serum and urine M-protein are not measurable, a decrease of <math>\geq 50\%</math> in the difference between involved and uninvolved FLC levels is required in place of the M-protein criteria
 
If serum and urine M-protein are not measurable, and serum free light assay is also not measurable, <math>\geq 50\%</math> reduction in bone marrow PCs is required in place of M-protein, provided baseline bone marrow plasma cell percentage was <math>\geq 30\%</math>
 
 |
| Stable disease (SD)   | 
 
Not meeting criteria for CR, VGPR, PR, or symptomatic MM
 
  |
| 
FLC = free light chain; PC = plasma cell
 
All response categories (CR, sCR, VGPR, PR) require 2 consecutive assessments made at any time before the institution of any new therapy and no known evidence of progressive or new bone lesions if radiographic studies were performed. VGPR and CR categories require serum and urine studies regardless of whether disease at baseline was measurable on serum, urine, both, or neither.
 
Radiographic studies are not required to satisfy these response requirements. Bone marrow assessments need not be confirmed.
 
*Clarifications to IMWG criteria for coding CR and VGPR in subjects in whom the only measurable disease is by serum FLC levels: CR in such subjects indicates a normal FLC ratio of 0.26 to 1.65 in addition to CR criteria listed above. VGPR in such subjects requires a <math>>90\%</math> decrease in the difference between involved and uninvolved FLC levels.
 
a Presence/absence of clonal cells is based upon the kappa/lambda ratio. An abnormal kappa/lambda ratio by immunohistochemistry or immunofluorescence requires a minimum of 100 plasma cells for analysis. An abnormal ratio reflecting presence of an abnormal clone is kappa/lambda of <math>>4:1</math> or <math><1:2</math>.
 |   |

### 9.2.1.2. Assessment of Disease Progression to Multiple Myeloma

For data analysis and reporting, the sponsor will use a computer algorithm to objectively and consistently implement the IMWG diagnostic criteria for MM requiring systemic therapy. During the study, disease progression will be measured according to the published international uniform diagnostic criteria for MM requiring systemic therapy established by the IMWG (Rajkumar 2014) presented in Table 5.

**Table 5: Diagnostic Criteria for Multiple Myeloma Requiring Systemic Therapy**

|  |
|--|
| 
Clonal bone marrow plasma cells <math>\geq 10\%</math> or biopsy-proven bony or extramedullary plasmacytomaa PLUS 1 or more of the following:
 
 
• Calcium elevation (<math>>0.25</math> mmol/L [<math>>1</math> mg/dL] higher than ULN or <math>>2.75</math> mmol/L [<math>>11</math> mg/dL])
 
• Renal insufficiency (creatinine clearanceb <math><40</math> mL/min or serum creatinine <math>>177</math> <math>\mu</math>mol/L [<math>>2</math> mg/dL])
 
• Anemia (hemoglobin <math><10</math> g/dL [<math><6.5</math> mmol/L] or <math>>2</math> g/dL [<math>>1.25</math> mmol/L] lower than LLN)
 
• Bone disease (one or more osteolytic lesions on skeletal radiography, CT, or PET-CTc)
 
• Clonal bone marrow plasma cell percentagea <math>\geq 60\%</math>
 
• Involved:uninvolved serum free light chain ratiod <math>\geq 100</math>
 
• <math>>1</math> focal lesione on MRI studies
 
 
a. Clonality should be established by showing <math>\kappa/\lambda</math> light-chain restriction on flow cytometry, immunohistochemistry, or immunofluorescence. Bone marrow plasma cell percentage should preferably be estimated from a core biopsy specimen; in case of a disparity between the aspirate and the core biopsy, the highest value should be used.
 
b. Measured or estimated by validated equations.
 
c. If bone marrow has less than 10% clonal plasma cells, more than one bone lesion is required to distinguish from solitary plasmacytoma with minimal marrow involvement.
 
d. These values are based on the serum Freelite assay (The Binding Site Group, Birmingham UK). The involved free light chain must be <math>\geq 100</math> mg/L.
 
e. Each focal lesion must be 5 mm or more in size.
 
From Rajkumar 2014
 |
|--|

Progressive disease must be documented consistently across clinical study sites using the same criteria. Disease progression based on 1 of the laboratory tests alone must be confirmed by at least 1 repeat investigation. It is important that instances of progression be reported to the sponsor as soon as possible.

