#### 4.2. Exclusion Criteria

Any potential subject who meets any of the following criteria will be excluded from participating in the study.

1. Active MM, requiring treatment, defined by any of the following:
  1. Bone lesions (one or more osteolytic lesions on skeletal radiography, computed tomography (CT), or positron-emission tomography [PET]-CT)
  3. Hypercalcemia (serum calcium  $>0.25$  mmol/L ( $>1$  mg/dL) higher than ULN or  $>2.75$  mmol/L ( $>11$  mg/dL))
  2. Renal insufficiency (see Section 9.2.1.4; preferably determined by creatinine clearance  $<40$  mL/min measured or estimated using validated equations [MDRD or CKD-EP formulae recommended], or serum creatinine  $>177$   $\mu$ mol/L [ $>2$  mg/dL])
  3. Anemia, defined as hemoglobin  $<10$  g/dL and/or  $>2$  g/dL below LLN in the absence of transfusion support or concurrent treatment with erythropoietin stimulating agents (ESAs)
  4. Clonal bone marrow plasma cell percentage  $\geq 60\%$
  5. Serum free light chain involved:uninvolved ratio  $\geq 100$
  6. More than 1 focal lesion by magnetic resonance imaging (MRI)
2. Primary systemic AL (immunoglobulin light chain) amyloidosis
3. Criterion modified per Amendment INT-2.

3.1 Prior or concurrent exposure to any of the following:

- To approved or investigational treatments for SMM or/and MM (including but not limited to conventional chemotherapies, immunomodulatory drugs (IMiDs), or proteasome inhibitors).
  - To daratumumab or other anti CD-38 therapies
  - To concurrent treatment with corticosteroids with a dose >10 mg prednisone per day or equivalent.
  - To concurrent treatment with bone-protecting agents (eg, bisphosphonates, denosumab) for treatment of SMM or MM. The subjects who are on a stable dose of these medications for a nonmalignant condition are allowed in the study.
  - Received an investigational drug (including investigational vaccines) or used an invasive investigational medical device within 4 weeks before Cycle 1, Day 1
4. Subject has a history of malignancy (other than SMM) within 3 years before the date of randomization, except for the following if treated and not active: basal cell or nonmetastatic squamous cell carcinoma of the skin, cervical carcinoma in situ, ductal carcinoma in situ of breast, or International Federation of Gynecology and Obstetrics (FIGO) Stage 1 carcinoma of the cervix.

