#### 9.2.1.4. CRAB Criteria-Related Laboratory Assessments

The following laboratory tests must be performed at every disease assessment, including during the follow-up period, whenever disease assessments are required:

- Serum calcium corrected for albumin (central lab)
- Creatinine clearance or serum creatinine (local lab)
- Hemoglobin (local lab)

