## Hemoglobin

Development of anemia (according to CRAB criteria; hemoglobin <10 g/dL or >2 g/dL lower than LLN) indicates progression to symptomatic MM if it is not attributable to any other cause. Before PD is declared on the basis of anemia without other CRAB signs or symptoms, additional diagnostic tests should be carried out to determine that there is no other underlying cause of anemia. Hemoglobin will be analyzed locally as part of the safety laboratory evaluations during treatment. For subjects who discontinue treatment prior to PD, these measurements should continue to be analyzed locally every time disease assessments are performed.

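### Table 5 prints two different absolute hemoglobin cut-offs for progression (10 g/dL and 6.5 mmol/L, about 10.4 g/dL), and neither document names the unit that governs

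*Protocol*

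**What the plan says.** Protocol Table 5 (Section 9.2.1.2) lists the criteria by which progression to multiple myeloma is measured. Its anemia line has two limbs, each in two units. The absolute limb reads "Anemia (hemoglobin <10 g/dL [ <6.5 mmol/L". The relative limb is more than 2 "g/dL [ >1.25 mmol/L] lower than LLN".

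Three other places bear on it:

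- Section 9.2.1.4, under Hemoglobin, repeats the rule in g/dL only: "Development of anemia (according to CRAB criteria; hemoglobin <10 g/dL or >2 g/dL lower than LLN) indicates progression to symptomatic MM", provided no other cause explains it.
- Section 4.2 excludes subjects with active myeloma, including "Anemia, defined as hemoglobin" below 10 g/dL and/or more than 2 "g/dL below LLN in the absence of transfusion support or concurrent treatment with erythropoietin stimulating agents (ESAs"). It gives no mmol/L figure.
- Section 9.2.1.4 assigns the test to local laboratories: "Hemoglobin (local lab").

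For the analysis, Section 9.2.1.2 says that "the sponsor will use a computer algorithm to objectively and consistently implement the IMWG diagnostic criteria for MM requiring systemic therapy". The text under Table 5 asks for progression to be documented on the same criteria at every site. Neither the protocol nor the SAP states a common hemoglobin unit for sites or for the algorithm.

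**The concern.** If the two bracketed figures on one line convert the same analyte by different factors, at least one of them does not express the g/dL value beside it. A site or program that works in mmol/L would then apply a different absolute threshold from one that works in g/dL.

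Table 5 feeds several results. Progression is an event in the co-primary PD/death rate (Protocol Section 9.2.2.1; SAP 5.2.1) and in PFS (Protocol Section 9.2.2.2; SAP 5.3.3). SAP 5.3.3.2 adds a PFS analysis by investigator assessment. Since Amendment 5, Attachment 4 has disease evaluated locally and progression determined by the investigator, so later events rest on how each site reads the criteria. Progression is also a reason for stopping study treatment (Section 10.3), which is a further reason for the text to carry a single threshold.

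**Working it through.** **Inputs, all from Table 5:** 10 g/dL paired with 6.5 mmol/L; 2 g/dL paired with 1.25 mmol/L.

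1. Factor implied by the absolute pair: 6.5 / 10 = 0.65 mmol/L per g/dL.
2. Factor implied by the relative pair: 1.25 / 2 = 0.625 mmol/L per g/dL.
3. Cross-check: at 0.65, 2 g/dL would be 2 × 0.65 = 1.30 mmol/L, not the printed 1.25. The line contradicts itself without any outside source.
4. With the relative pair's factor: 10 × 0.625 = 6.25 mmol/L, and 6.5 / 0.625 = 10.4 g/dL. The gap is 0.4 g/dL.

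**Can rounding explain it?**

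- If 1.25 stands for anything from 1.245 to 1.255, the factor is 0.6225 to 0.6275. Then 10 g/dL is 6.225 to 6.275 mmol/L, and 6.5 mmol/L is 10.36 to 10.44 g/dL.
- If 6.5 stands for anything from 6.45 to 6.55, at 0.625 it is 10.32 to 10.48 g/dL.
- With both roundings at their most favorable, 6.45 / 0.6275 = 10.28 g/dL, still above 10.

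**Is the whole table affected?** Calcium is the other analyte with two pairs: 0.25 / 1 = 0.25 and 2.75 / 11 = 0.25 mmol/L per mg/dL. These agree. The inconsistency found is between the two hemoglobin pairs.

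**When does the gap matter?** The relative limb already counts any value below LLN − 2. The mmol/L bracket therefore adds something only where LLN − 2 < 10.4, that is, LLN < 12.4 g/dL. The same limit applies to overlap with eligibility, because Section 4.2 admits a subject on hemoglobin when the value is at least max(10, LLN − 2). The documents give no LLN, so the values below are assumed.

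| Assumed LLN (g/dL) | Lowest eligible hemoglobin (g/dL) | Eligible range that also meets <6.5 mmol/L |
|---|---|---|
| 11.0 | 10.0 | 10.0 to <10.4 |
| 12.0 | 10.0 | 10.0 to <10.4 |
| 12.4 | 10.4 | none |
| 13.0 | 11.0 | none |
| 14.0 | 12.0 | none |

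Example: 10.2 g/dL is 10.2 × 0.625 = 6.375 mmol/L. With an LLN of 12.0 g/dL, that value passes Section 4.2 and does not meet the g/dL limbs of Table 5, but it meets the mmol/L bracket.

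**The case against.** The best reply is that the slip need not reach the primary result. A reader might infer that the co-primary progression threshold does differ by local laboratory unit. The documents do not support that. Section 9.2.1.2 provides one sponsor algorithm for analysis and reporting, and nothing says that it uses mmol/L. Nothing shows that any site reports hemoglobin in mmol/L either. If all values are standardized to g/dL, the algorithm-derived PD/death rate is untouched, and only investigator-assessed progression and site decisions are exposed. This stands, and it is why the effect on the co-primary is stated conditionally.

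The second reply is that a low value alone does not make a progression event. Table 5 also needs clonal marrow plasma cells of at least 10% or a biopsy-proven plasmacytoma, and a progression based on one laboratory test needs a repeat. Section 9.2.1.4 asks for other causes of anemia to be ruled out, and speaks of anemia developing, which a subject who enters at 10.2 g/dL and stays there has arguably not done. Section 10.3 has the medical monitor confirm discontinuation. These safeguards limit the number of events, but they do not remove the inconsistency. A repeat filters noise, not a shifted cut-off: a stable 10.2 g/dL is below 6.5 mmol/L each time. Marrow plasma cells of at least 10% are already required at entry (Section 4.1), so that condition may screen out few subjects. Ruling out other causes addresses attribution, not the threshold.

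A reader might also simulate a subject sitting just above 10 g/dL, find a high chance of two consecutive readings under 6.5 mmol/L, and take it as a rate of false progression. It is not one. It is conditional on an assumed subject near the cut-off and leaves out attribution and the reporting unit. The documents do not say how many subjects lie in that range.

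**Conclusion.** The inconsistency is real and is shown by Table 5 alone. The printed absolute cut-offs differ by about 0.4 g/dL on the table's own second conversion, and rounding does not close the gap. The mmol/L bracket also conflicts with the g/dL-only rule in Section 9.2.1.4 and with the exclusion in Section 4.2. With local measurement and no stated unit, the same-criteria requirement under Table 5 is not secured.

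The consequence is conditional. Investigator-assessed progression and PFS could be affected wherever a result is read against the mmol/L bracket. The co-primary PD/death rate could be affected only if the algorithm applies that value. Both need a local LLN below about 12.4 g/dL, so it would be wrong to infer that the progression criterion overlaps the eligible range in general. The number of affected events cannot be computed from the documents and is probably small. The stated power and sample size do not depend on this conversion.

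A reader might also conclude that one of the two figures is the correct clinical threshold. This review takes no view on that. The passages disagree and must be reconciled.

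**What to change.** Make three changes.

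1. Reconcile the two hemoglobin brackets in Table 5 with Section 9.2.1.4 and the Section 4.2 exclusion, so that g/dL and mmol/L express one threshold throughout.
2. State in the algorithm specification a single unit to which all local hemoglobin values and local LLNs are converted before the criterion is applied.
3. As a sensitivity analysis, list any progression based on anemia alone with hemoglobin of 10.0 to 10.4 g/dL, and show the PD/death rate and PFS with those events handled under the reconciled threshold.

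Hemoglobin is already collected, so no new data are needed. The cost is a text correction, one line in the specification and a small amount of extra analysis. The Amendment 5 rationale records that the primary analysis has already been described in a study report. Editing Table 5 cannot change that result, so the third step is the one that would show whether the discrepancy touched it.
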